## Adjustment for Multiple Comparisons

The Hochberg procedure will be applied to control for multiplicity for each of the primary and secondary hot flash related endpoints. Each endpoint will have 4 analyses associated with them to account for the two active dose arms (10 mg and 50 mg) each compared to baseline by two methods each (MMRM test for slope and MMRM test for change from baseline at the specified week). These may be referred to as sets of analyses. Hochberg is a step-up procedure based on univariate p-values. This procedure begins

with the least significant p-value and then examines the other p-values in sequential order, making alpha level adjustments along the way, until a significant p-value is observed. Once achieved, all following lower p-values in the sequence would be considered significant. For example, if one has 4 hypotheses the following will be performed:

- Step 1: Order the p-values from largest (least significant) to smallest (most significant)
- Step 2: Using the pre-specified overall alpha level,  $\alpha_0=0.10$ , one-sided, compare the largest p-value, P1, to the overall alpha level. If P1<0.10 then all (null) hypotheses are rejected; otherwise go to step 3.
- Step 3: Compare the second largest p-value, P2, to  $\alpha_1$ =0.10/2=0.05. If P2<0.05 then this and all further hypotheses are rejected; otherwise repeat for the third, P3, and fourth, P4, largest p-values compared with  $\alpha_2$ =0.10/3=0.033 and  $\alpha_3$ =0.10/4=0.025 as necessary to either reject all remaining hypotheses or conclude no significant difference exists.

For this study, during Stage 1, Hochberg's procedure will rank the p-values from highest to lowest for each statistical test within each set of analyses: 10 mg versus placebo slope difference (through Week 6), 50 mg versus placebo slope difference (through Week 6), 10 mg versus placebo mean difference at week 6, 50 mg versus placebo mean difference at Week 6. Adjustment for the single comparison of 100 mg versus placebo in Stage 2 will be necessary only for the two MMRM modes, means and slopes.

Overall, for the multiple tests of primary and secondary endpoint analyses alpha control will be achieved by a gate-keeping method such that the endpoints are ordered and the preceding endpoint must be shown to be significant in order for endpoints down the list to be eligible for significance.

The order of the secondary endpoint assessments will be:

- 1. Percentage change in severity of vasomotor symptoms from baseline to Weeks 6 (Day 42)
- 2. Percentage change in frequency of moderate to severe vasomotor symptoms from baseline to Week 8 (Day 56)
- 3. Percentage change in frequency of moderate to severe vasomotor symptoms from baseline to Week 10 (Day 70)
- 4. Percentage change in frequency of moderate to severe vasomotor symptoms from baseline to Week 12 (Day 84)
- 5. Percentage change in severity of vasomotor symptoms from baseline to Week 8 (Day 56)
- 6. Percentage change in severity of vasomotor symptoms from baseline to Week 10 (Day 70)
- 7. Percentage change in severity of vasomotor symptoms from baseline to Week 12 (Day 84)
- 8. Percentage change in frequency of moderate to severe vasomotor symptoms from baseline to Week 4 (Day 28)
- 9. Percentage change in severity of vasomotor symptoms from baseline to Week 4 (Day 28)
- 10. Percentage change in bone turnover marker concentrations at Day 84 compared with baseline

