## 6. STATISTICAL METHODOLOGY

## 6.1 Statistical and Analytical Issues

## 6.1.1 Statistical Methods

For quantitative variables, descriptive statistics will include the number of subjects (n), mean, standard deviation (SD), median, minimum and maximum. Categorical variables will be summarized using the number (n) and percentage (%) of subjects for each category. Unless otherwise specified, the denominator for all percentages will be the number of subjects in the respective treatment group who have data for the respective time point in the applied analysis population. Percentage change from baseline will be calculated using the non-missing (see section 6.1.2) data of both baseline and the respective post-baseline value.

The primary efficacy analyses will only include efficacy data that were captured in the eDiary for hot flashes which were treated with study drug (VERU-944 or placebo). All baseline measurements for efficacy will be collected prior to dosing in the treatment period. By default the frequency and severity of hot flashes at baseline will be determined from the second week of the first two weeks of hot flash eDiary that were recorded; If a patient qualified for the study entry by number of hot flashes during the second week of screening, then data from that week will be used as their baseline. However, if a patient did not qualify for study entry based on the number of hot flashes during that second week then data from the screening week that was used to qualify the patient will be used as their baseline instead. Percentage change from baseline is defined as the post-baseline value of interest minus the baseline value then divided by the baseline value and finally converted to a percentage by multiplying by 100.

A 1-sided alpha level equal to 0.10 will be used to determine statistical significance for the primary and secondary efficacy objectives related to hot flash frequency and severity.

For the treatment period, baseline for the safety assessments will be defined as the Day 1 assessment, or if missing, the last assessment prior to dosing.

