#### 6.3.2.10 Bone Marker Turnovers

## STAGE 1:

The secondary efficacy endpoint for bone marker turnovers is percentage change in bone turnover marker concentrations at Day 84 compared with baseline (Day 1, pre-dose). The bone markers to be assessed will include: serum C-telopeptide and bone specific alkaline phosphatase. For each marker, the mean, SD, median, minimum, and maximum will be summarized at each time point by treatment. The percentage change from baseline to Day 84 will also be summarized.

The t-test or the Wilcoxon rank-sum test, if the data are determined to be non-normally distributed, will be used for between group treatment comparisons comparing the percentage change from baseline in the placebo arm to the percentage change from baseline in each treatment group (10 mg and 50 mg) at Day 84. The paired T-test or the Wilcoxon signed-rank test, if the data are determined to be non-normally distributed, will be used for comparing baseline and Day 84 within each treatment group. Analyses will be conducted on the ITT population.

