#### 6.7 Interim Analysis

During Stage 1, after the last subject has completed the Day 42 visit, an unblinded interim analysis (IA) of the Week 6 (Day 42) hot flash primary endpoint (frequency) and first secondary endpoint (severity) of VERU-944 will be conducted. A blinded analysis of the safety will also be conducted. Both the Sponsor and CRO study team will remain blinded to patient level data until completion of the study stage. An

unblinded statistical support group, independent of the study team (within the CRO), along with a representative of Veru Inc., will review the IA results and determine steps forward. It is of note that due to the material nature of the IA results of this study in the business of Veru Inc., a publicly traded company, these results may be required to be released in a press release prior to the completion of Stage 1 of this study.

The analyses to be included in the IA will be the analyses of hot flash frequency at Week 6 (Section 6.3.1.1) and the hot flash severity at Week 6. These analyses will include the summary statistics and MMRM model for both the ITT and EEIA populations. The sensitivity analyses associated with these sections will not be conducted during the IA.

In addition to the efficacy analyses, a blinded safety report will be reviewed to assess drug safety. All IA analyses will be conducted on the EEIA population.

If an effective dose of VERU-944 is achieved in Stage 1, as defined as a statistically significant result), the Sponsor reserves the right to not initiate Stage 2 of the protocol. However, if an effective dose is not achieved in the Stage 1 IA, then the study will commence with Stage 2.

Regardless of IA outcome, unless safety issues are observed, the Stage 1 section of the study will continue to completion at 12 Weeks with Follow-up.

Assuming Stage 2 is implemented, an additional replicate IA will be conducted after the last subject in Stage 2 has completed the Day 42 visit. This IA will follow the same procedures as done for Stage 1.

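### The gate across endpoints never says when an endpoint with four tests counts as significant, nor which dose may pass, so the claimed alpha control is not secured

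*SAP*

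**What the plan says.** SAP 6.1.1 sets the level: "A 1-sided alpha level equal to 0.10 will be used to determine statistical significance for the primary and secondary efficacy objectives"; the sentence goes on to confine this to hot flash frequency and severity. Under Adjustment for Multiple Comparisons in SAP 6.3.1, "Each endpoint will have 4 analyses associated with them to account for the two active dose arms", each tested by an MMRM mean and an MMRM slope. Hochberg runs within each set of four at 0.10, 0.05, 0.033 and 0.025. It can reject only part of a set: "Once achieved, all following lower p-values in the sequence would be considered significant".

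Across endpoints, the SAP says of the "primary and secondary endpoint analyses alpha control will be achieved by a gate-keeping method", the rule being that "the preceding endpoint must be shown to be significant in order for endpoints down the list to be eligible for significance". The list follows under "The order of the secondary endpoint assessments will be": nine hot flash endpoints, then bone turnover markers as item 10. With the primary endpoint, that makes ten Hochberg sets plus the bone markers.

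SAP 6.7 has a success criterion for the decision on Stage 2: "If an effective dose of VERU-944 is achieved in Stage 1, as defined as a statistically significant result", in which case the sponsor may choose not to start Stage 2. On bone markers, SAP 6.3.2.10 says: "The bone markers to be assessed will include: serum C-telopeptide and bone specific alkaline phosphatase", each compared between placebo and both doses, with no multiplicity step.

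Protocol 9.3.1.1 and 9.3.2.1 have Hochberg within endpoints only and no gate; Protocol 9.3.2.1 refers to the SAP for the full analyses.

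**The concern.** A gate in a fixed sequence protects the error rate only if a failed hypothesis stops what comes after it. Here the gate is attached to the endpoint, but the claims are made per dose and per method. Hochberg can leave an endpoint with one, two or three of its four tests rejected, and the SAP does not say whether that endpoint has then passed. If it has, the dose that passed carries the dose that failed on to the next endpoint, where the failed dose gets a new test at the full level.

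The setting in which this bites is one active and one inactive dose, which is a central possibility in a trial meant to find an effective dose. The first two links, frequency and severity at Week 6, are the analyses reported at the unblinded interim, and SAP 6.7 notes that those results may have to be made public before Stage 1 ends. With the rule undefined, it could also be settled after the p-values are known.

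**Working it through.** **The plan's own figures.** Hochberg steps for four tests are 0.10/k for k = 1 to 4: 0.10, 0.05, 0.033, 0.025. These match the SAP. Error at the first endpoint alone is at or below 0.10 in every scenario run (0.079 to 0.098).

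**Mechanism under the any-test reading.** Suppose both 50 mg p-values are very small. The two 10 mg p-values are then the largest of the four and meet the 0.10 and 0.05 steps. A false 10 mg claim occurs if the larger 10 mg p-value is below 0.10 or the smaller is below 0.05. With an assumed mean-slope correlation of 0.7 this has probability about 0.09. Because 50 mg opens every gate, the same risk recurs at each endpoint, whatever 10 mg did before.

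**Accumulation over the list.** The documents give no correlations, so these are assumptions: 0.7 between mean and slope, and a common correlation between endpoints (the product of the two for different tests at different endpoints). One-sided z-tests, 200,000 simulated trials, 50 mg certain to win, 10 mg inactive:

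| Correlation between endpoints | 1 endpoint | 2 (Week 6 frequency and severity) | 4 | 10 |
|---|---|---|---|---|
| 0.9 | 0.09 | 0.12 | 0.15 | 0.19 |
| 0.3 | 0.09 | 0.16 | 0.27 | 0.46 |

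For reference, ten independent tests at 0.10 give 1 − 0.9^10 = 0.651.

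**A second model.** Weekly arm means were simulated over 12 weeks for frequency and severity, with the mean contrast and linear slope through each week. Five correlation settings were used (between-subject share 0 to 0.8, AR(1) 0.3 to 0.8, frequency-severity correlation 0 to 0.8). The entries are the chance of at least one false claim over the ten hot flash endpoints:

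| Gate rule | Neither dose works | 50 mg certain, 10 mg inactive | 50 mg at 90% power per test, mean and slope | 50 mg at 90% power, mean only |
|---|---|---|---|---|
| Any of the four tests | 0.079–0.087 | 0.305–0.546 | 0.269–0.340 | 0.223–0.260 |
| All four tests | 0.079–0.087 | 0.091–0.098 | 0.089–0.093 | 0.085–0.089 |
| Same dose, any of its tests, no alpha split | 0.079–0.087 | 0.091–0.098 | 0.089–0.093 | 0.157–0.175 |
| Per dose at 0.05, Hochberg within dose, both tests required | 0.081–0.088 | 0.046–0.049 | 0.046–0.049 | 0.086–0.089 |

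The 90% power is per test at one-sided 0.10. The third row shows that tying the gate to the dose is not enough by itself.

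**Stage 2.** Each endpoint has two tests, mean and slope. Under the any-test reading, with a certain mean effect and no slope effect, the chance of at least one false slope claim over ten endpoints is 0.333 to 0.482.

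**Bone markers.** Two markers by two doses make four tests. No alpha is stated for them. If each were tested at an assumed one-sided 0.10 with no true effect, the chance of a false claim would be 1 − 0.9^4 = 0.344 if independent, and about 0.26 at a common correlation of 0.5. This applies only if the gate reaches item 10, so it cannot simply be added to the figures above.

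**The case against.** A reader might infer that the SAP lets any one of four tests open the gate, and so that alpha control is lost outright. The documents do not support that. The gate sentence speaks of the preceding endpoint and says nothing of any or all tests. The criterion in SAP 6.7, one statistically significant result, fits the any-test reading but belongs to the decision on Stage 2 and does not define the gate. If all four tests must reject, the error stays below 0.10 throughout.

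The inflation is also conditional. It needs one dose, or one of the two methods, to be active and the other not; when neither dose works the error is at most 0.087. The primary endpoint by itself is protected. The figure over ten endpoints therefore says nothing about the decision on Stage 2, which rests on the two Week 6 endpoints. Nor do the documents say that a false 10 mg claim is the costliest error.

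The size depends on assumed correlations and on treating every test as a one-sided z-test. SAP 6.3.1.1 takes the slope result from the overall interaction p-value plus a check of direction. If that p-value is two-sided and not halved, the first model gives about 0.15 to 0.36 over nine endpoints, lower but still above 0.10.

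All of this limits the point without removing it. A plan that controls alpha under one permitted reading and not under another has not prespecified control, and no other section supplies the missing rule.

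**Conclusion.** The concern holds as a gap in the rule. The SAP claims alpha control from a gate that does not define a significant endpoint and is not linked to the dose that passed. Under the permitted any-test reading, with 50 mg certain to win and 10 mg inactive, the chance of at least one false 10 mg claim is about 0.12 to 0.16 after two endpoints and 0.19 to 0.46 over ten, against 0.10. Those ranges assume a mean-slope correlation of 0.7 and endpoint correlations from 0.9 down to 0.3; other assumed structures reach about 0.55, and 90% power for 50 mg on both tests gives 0.27 to 0.34. Every setting run with only 50 mg active exceeds 0.10 under this reading. The bone-marker gap is separate and smaller. The change should be made, because one paragraph makes the SAP's own claim true.

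**What to change.** Replace the gate sentence in SAP 6.3.1 with one explicit rule, either:

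- **(a) A sequence per dose.** Give each dose one-sided 0.05. At each endpoint apply Hochberg to that dose's mean and slope tests (0.05, 0.025). The dose moves on only if both are rejected. Hochberg within the dose must be written down: with both doses inactive, mean-slope correlation 0.7 and an assumed dose correlation of 0.5, running each test at 0.05 gives about 0.14, while Hochberg gives about 0.08.
- **(b) A gate on the whole set.** Keep the four-test Hochberg sets and open the next endpoint only if all four tests were rejected. Otherwise label later p-values nominal.

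In Stage 2, require both the mean and the slope test to be rejected before moving on.

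For bone markers, state an alpha and apply Hochberg across the four Stage 1 tests, or label them descriptive.

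The cost is one SAP paragraph and some formal claims. Option (a) holds each dose to a stricter level, so a p-value between 0.05 and 0.10 no longer counts even when both doses do well. Option (b) usually blocks formal secondary claims for a working 50 mg dose when 10 mg is inactive: all four tests can reject only if both 10 mg p-values fall below 0.10, which has probability at most 0.10. If claims for a single working dose matter, (a) is the better choice.

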#### Common analytical methods for all hot flash related analyses

The MMRM analyses shown in the following section with SAS code written specifically to address the primary analysis of difference in percentage change of the frequency of hot flashes at Week 6 between each of the active arms and placebo are the **SAME** for all hot flash related analyses, both frequency and severity, at all weeks of interest. Simple changes to the data set to subset to the appropriate weeks of data and to the LSESTIMATE statements are all that is necessary to construct the appropriate tests. MMRM models that test for MEAN difference between active arm(s) at Week 6 and placebo and separately for a

difference in SLOPE between active arm(s) at Week 6 and placebo. There is no plan to compare the active arms to each other.

If the MMRM models does not converge or have poor fit, T-tests or non-parametric tests, if the data are deemed non-normally distributed, will compare percentage changes over time between (T-test or Wilcoxon rank sum test) each active arm and the placebo arm, respectively.

## 6.3.1.1 Primary Efficacy Endpoint Analysis (Hot Flash Frequency at Week 6)

STAGE 1:

The primary frequency efficacy endpoint is percentage change in frequency of moderate and severe hot flashes (vasomotor symptoms) from the baseline week to Week 6 (Day 42). The statistical tests for significant differences with regards to the percentage change between placebo and each of the active arms, 10 mg 50mg, and perhaps 100 mg comprise the main tests of interest.

The SAS code for performing the MMRM analyses to test for a significant difference in the MEAN percentage change in frequency of moderate to severe hot flashes between each of the dose arms and placebo evaluated at Week 6 (primary analysis week) is shown below. Note that this analysis will generate two of the four tests that are part of the primary analysis to which the Hochberg procedure will apply.

PROC MIXED DATA= XXX; CLASS subjid tx week; MODEL cfb = tx week\_2 tx\*week\_2; REPEATED week / type=AR(1) sub=subjid(tx); LSESTIMATE tx\*week '10MG VS Placebo at Week 6' [1, 10 6] [-1, P 6]; LSESTIMATE tx\*week '50MG VS Placebo at Week 6' [1, 50 6] [-1, P 6]; WHERE week le 6; RUN;

The variables used in the above model will be defined as follows: tx=treatment; week (1, 2... 6); cbf=change from baseline value, week\_2=week (week will be treated as a categorical variable in the class statement and week\_2 will be treated as a continuous variable in the model... effectively the values of these variables will be an exact match). By creating week\_2 in a preceding data step, this allows for LESTIMATES to be computed at a specific WEEK (treated as categorical in the CLASS statement) but allows week to be treated as a continuous variable, WEEK\_2 in the model.

This model will be run 3 separate times using 3 separate covariance structures to determine best fit. The same model will be run, with the following specified change on the REPEATED line: (1) type=AR(1); (2) type=CS; and (3) type=UN. If a model does not converge, then disregard that model. If more than 1 model remains, then refer to the Akaike's Information Criteria (AIC) score to determine model fit. The best fit model will be chosen as having the AIC value closest to zero. The model type chosen will be referenced in the footnote for each model output.

Additional prespecified analysis of the data will be conducted regardless of whether the MMRM model(s) converge, and will be considered the definitive tests for significance in the event the MMRM model(s) do not converge:

• T-tests will be generated to compare the percentage change from baseline to each of Week 6 in the placebo arm to each of the 10 mg and 50 mg arms. If the data are determined to be non-normally distributed then the Wilcoxon rank sum test will be the definitive test of significance.

• Wilcoxon rank sum tests will be generated to compare the percentage change from baseline to Week 6 in the placebo arm to each of the 10 mg and 50 mg arms.

The SAS code for performing the MMRM analyses to test for a significant difference in the SLOPES of the percentage change in frequency of moderate to severe hot flashes between each of the dose arms and placebo by Week 6 (primary analysis week) is shown below. Note that these analyses will generate the remaining two of the four tests that are part of the primary analysis to which the Hochberg procedure will apply.

The where statement in PROC MIXED has been used to simplify the interpretation of the output so that one model will be run for the 10 mg versus placebo slope analysis and a separate one for the 50 mg versus placebo slope analysis through Week 6. Variable have the same meaning as defined in the above analysis.

PROC MIXED DATA=XXX; CLASS subjid tx; MODEL cfb= tx week tx\*week / s; RANDOM intercept week/ type=AR(1) sub=subjid g; WHERE tx in (10, P) and week le 6; /\* repeat for 'tx in (50, P)' \*/ RUN;

This model allows for both the intercept and the slope to differ randomly for each subject but the overall p-value for the interaction term is interpreted as a test of the slope between the stated active arm and placebo. Note, if the p-value is significant, the estimated coefficients must be in the appropriate direction to conclude the result is in favor of the active dose arm.

